### 7.3. Analysis of the Secondary Efficacy Parameter

Secondary efficacy analyses will be conducted for the ITT population.

#### 7.3.1. European LeukemiaNet Response

Response status assessed by investigation based on the European LeukemiaNet (ELN) 2013 response criteria ([Appendix A](#)) will be collected on the eCRF.

The proportion of subjects who achieve CR or PR at Week 32 will be estimated with 95% confidence interval. The CMH test stratified by JAK2V617F mutation status (positive or negative), screening platelet count level ( $\geq 1000 \times 10^9/L$  or  $< 1000 \times 10^9/L$ ), and prior anagrelide use (yes vs no) will be applied to compare the 2 treatment groups. The overall stratum-adjusted odds ratio, along with its 95% confidence interval, will be presented.

The proportion of subjects with CR at Week 32 and the proportion of subjects with PR at Week 32 will be analyzed in a similar fashion to that above.

If no scheduled response status assessment at Week 32 is available, then assessment within a window of the target day (Day 225)  $\pm$  14 days will be used. Subjects with missing ELN response status at Week 32 will be considered as nonresponders.

If the JAK2V617F mutation status at randomization is not consistent with the JAK2V617F mutation status collected on the eCRF, an additional sensitivity analysis will be performed by stratifying the JAK2V617F mutation status collected on the eCRF, screening platelet count, and prior anagrelide use (yes vs no).

#### 7.3.2. Duration of Response

For subjects who achieve primary response as defined in Section [7.2.1](#), duration of response will be assessed using Kaplan-Meier method.

Duration of response is defined as the time from the start of response until the end of response. The start of a response will be the first visit where both platelet control (defined as a reduction to  $< 600 \times 10^9/L$ ) and WBC control (defined as a reduction to  $< 10 \times 10^9/L$ ) are achieved, provided that the platelet and WBC control are ongoing at the time of Week 32 if the start of the response is before Week 32. Loss of response will be defined as 2 consecutive visits where either platelet count is  $\geq 600 \times 10^9/L$  or WBC is  $\geq 10 \times 10^9/L$ . The earlier of the 2 consecutive visits will be used as the end of response time. Subjects who are still maintaining both platelet control and WBC control at the time of database freeze or discontinuation of study drug will be censored at the date of the last assessment (platelet and WBC). The duration of response should include the 12 consecutive weeks between Week 32 and Week 52 when the primary response defined in Section [7.2.1](#) is achieved.

For the calculation of duration of response, the evaluable scheduled assessments will be used. If no scheduled assessment is available, then the unscheduled assessment closest to the visit target day within the analysis window will be used. The following windows will be applied to the target day:

- On or before Week 52: +/- 7 days
- Week 56 and after: +/- 14 days

[figure not shown]

[figure not shown]
Missing platelet counts or WBC at a visit (with no scheduled visit and no unscheduled visit within window of target day) will be considered as not achieving platelet control and WBC control during that visit.

[figure not shown]

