##### **9.4.1.2. Secondary Efficacy Analyses**

Secondary efficacy analyses will be conducted for the ITT population.

- Proportion of subjects who achieve CR or PR at Week 32, as defined by ELN 2013 response criteria, will be estimated with a 95% confidence interval. The CMH test stratified by JAK2V617F mutation status (positive or negative), screening platelet count ( $\geq 1000 \times 10^9/L$  or  $< 1000 \times 10^9/L$ ), and prior anagrelide use (yes vs no) will be applied to compare the 2 treatment groups. The overall stratum-adjusted odds ratio along with its 95% confidence interval will be presented.

- Proportion of subjects who achieve CR or those who achieve PR (separate analyses) at Week 32, as defined by ELN 2013 response criteria, will be estimated with a 95% confidence interval. The CMH test stratified by JAK2V617F mutation status (positive or negative), screening platelet count ( $\geq 1000 \times 10^9/L$  or  $< 1000 \times 10^9/L$ ), and prior anagrelide use (yes vs no) will be applied to compare the 2 treatment groups. The overall stratum-adjusted odds ratio along with its 95% confidence interval will be presented.
- Duration of responses for subjects who achieve primary response as defined in the primary efficacy endpoint is defined as the time from the start of response until the end of response. The start of a response will be the first visit where both platelet control (defined as a reduction to  $< 600 \times 10^9/L$ ) and WBC control (defined as a reduction to  $< 10 \times 10^9/L$ ) are achieved. Loss of response will be defined as 2 consecutive visits where either platelet count is  $\geq 600 \times 10^9/L$  or WBC is  $\geq 10 \times 10^9/L$ . The earlier of the 2 consecutive visits will be used as the end of response time. Duration of response will be estimated using the Kaplan-Meier method.
- Proportion of subjects who achieve reduction of platelet count to  $< 600 \times 10^9/L$  for at least 80% of biweekly assessments for a consecutive 12-week period between Weeks 32 and 52 will be summarized along with their 95% confidence interval.
- Proportion of subjects who achieve reduction of WBC counts to  $< 10 \times 10^9/L$  for at least 80% of biweekly assessments for a consecutive 12 weeks period between Weeks 32 and 52 will be summarized along with their 95% confidence interval.

[REDACTED]

[REDACTED]

[REDACTED]

[REDACTED]

[REDACTED]

[REDACTED]

[REDACTED]

[REDACTED]

[REDACTED]

[REDACTED]

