### 7.2. Analysis of the Primary Efficacy Parameter

#### 7.2.1. Primary Efficacy Analysis

The primary efficacy endpoint is the proportion of subjects who achieve a simultaneous reduction of platelet counts to  $< 600 \times 10^9/L$  and of WBC counts to  $< 10 \times 10^9/L$  for at least 80% (6 out of 7 consecutive visits) of biweekly assessments for 12 consecutive weeks between Week 32 and Week 52. This analysis will be based on the ITT population according to the treatment assigned at randomization. The proportion of subjects who meet the response criteria will be estimated with 95% confidence interval. The CMH test stratified by JAK2V617F mutation status (positive or negative), screening platelet count ( $\geq 1000 \times 10^9/L$  or  $< 1000 \times 10^9/L$ ), and prior anagrelide use (yes vs no) will be applied to compare the 2 treatment groups. The test will be 2-sided at 5% significant level. The overall stratum-adjusted odds ratio, along with its 95% confidence interval, will be presented.

In the analysis of the primary efficacy endpoint, the evaluable scheduled assessments will be used. If no scheduled assessment is available, then the unscheduled assessment closest to the visit target day within the analysis window will be used. If there are 2 unscheduled assessments at the same distance to the target day, then the second one will be used for the evaluation. A window of the target day  $\pm 7$  days will be applied for all unscheduled visits. For example, the target day for Week 32 is at Day 225 ( $= 32 \times 7 + 1$ ).

Missing platelet counts or WBC counts at a visit (with no scheduled visit and no unscheduled visit within window of target day) in the range of at least 12 consecutive weeks of assessment of the primary endpoint will be considered as not achieving platelet control and WBC control during that visit. Subjects who discontinue study treatment without meeting the response criteria will be considered as nonresponders. Subjects who meet the primary endpoint criteria of a response but discontinue study drug before Week 52 will be considered as responders.

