### 11.1. Changes to Protocol-Defined Analyses

Not applicable.

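### SAP 7.3.2 turns two consecutive missed visits after the qualifying 12 weeks into a loss-of-response event, even when every observed count is controlled

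*SAP*

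**What the plan says.** Protocol 9.4.1.2 ends a response on measured values: "Loss of response will be defined as 2 consecutive visits where either platelet count is" at or above 600, or WBC is at or above 10. It has no rule for missing visits in this endpoint.

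SAP 7.3.2 repeats that definition and dates the event: "The earlier of the 2 consecutive visits will be used as the end of response time". It censors subjects who still maintain control at database freeze or study drug discontinuation, at their last platelet and WBC assessment. It also states: "The duration of response should include the 12 consecutive weeks between Week 32 and Week 52" in which the primary response was met.

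Its last paragraph deals with a visit that has no usable count, scheduled or unscheduled. It opens "Missing platelet counts or WBC at a visit (with no scheduled visit and no unscheduled visit within window of target day) will be considered", and completes the rule by saying that such a visit "will be considered as not achieving platelet control and WBC control during that visit". The window for unscheduled counts is 7 days either side of target up to Week 52 and 14 days from Week 56. SAP 11.1 gives the changes to Protocol-defined analyses as "Not applicable".

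**The concern.** Control means platelets below 600 and WBC below 10. A visit scored as not in control is therefore naturally read as a visit on the wrong side of the loss threshold, and two of them satisfy the loss rule. The SAP never says outright that two missed visits are a loss, but in a section that only computes duration the sentence has little other effect.

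Scoring a missing visit as failure is a familiar conservative choice for a yes/no response such as the primary endpoint. In a time-to-event analysis it creates an event with a date and discards any controlled counts that follow. The curve then mixes loss of control with attendance.

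The SAP separates the two elsewhere. In 7.2.3.1.1, a period is a nonresponse only if at least 2 visits have counts at or above the thresholds; a period left open by missing counts is nondeterminable. No comparable treatment of duration of response is visible in the public text, parts of which are redacted.

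**Working it through.** The documents state no event count, median or missed-visit rate for duration of response, so there is no figure to reproduce.

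**1. Where a false loss can arise.** SAP 7.2.1 requires 6 of 7 visits in control (6/7 = 85.7%; 5/7 = 71.4% falls short of 80%). At most one visit in the qualifying window can be missing, so a pair of missed visits cannot lie wholly inside it. It can only straddle the window's end or come later.

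**2. The rules applied to one subject.** Take a responder controlled at Weeks 32 to 44, with no count at Weeks 46 and 48.
- Controlled from Week 50 onward: measured counts give no event; the missing-visit rule gives an event at Week 46.
- Drug stopped just after Week 48: the missing-visit rule gives an event at Week 46; the censoring rule gives a censored time at Week 44. Two programmers could produce different curves from the same text.

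**3. Size.** Assumptions: true counts always in control, each visit missed independently with probability q, no rescue by an unscheduled count. Visits are every 2 weeks from Week 32 to 52 (11 visits), then Weeks 56, 68, ... 152 (9 visits), following the Protocol schedule.

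Hand check to Week 52: if Weeks 32 to 44 are complete, four visits remain (Weeks 46 to 52). The probability of at least one adjacent missing pair is 3q² − 2q³:
- q = 3%: 0.0027 − 0.000054 = 0.26%
- q = 5%: 0.0075 − 0.00025 = 0.73%
- q = 10%: 0.030 − 0.002 = 2.8%

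Exact version: all 2^11 = 2,048 missing patterns for Weeks 32 to 52 were enumerated, the 6-of-7 rule applied and the first qualifying window taken. Any adjacent missing pair from that window onward was counted, including one straddling its end. Results are conditional on being a responder.

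For the 9 later visits, let a be the probability of no event so far with the last visit present, and b the same with the last visit missing. Each visit updates a to (a + b)(1 − q) and b to a·q; the remainder is the event probability.

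| Missed per visit (assumed) | By Week 52 | To Week 152 |
|---|---|---|
| 3% | 0.3% | 1.1% |
| 5% | 0.9% | 3.0% |
| 10% | 3.1% | 10.8% |

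If loss needs two measured raised visits, each entry is 0 by construction. The table leaves out the second route, one missed visit beside a single raised count.

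**4. In subjects.** The design rates (30% and 5% of 60 per group) imply 18 + 3 = 21 responders. At 5% missed visits the expected number of false losses is 21 × 0.0088 = 0.2 by Week 52, and 21 × 0.030 = 0.6 if all were followed to Week 152. At 10% it is 21 × 0.031 = 0.65 and 21 × 0.108 = 2.3.

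**The case against.** **The Protocol is not contradicted.** A reader might infer that the SAP overrides the Protocol's definition and that the entry in 11.1 is therefore false. The documents do not support this. The Protocol is silent on missing visits here, the SAP repeats its loss definition, and SAP 4.1.5 lets individual sections set missing-data rules. The conflict that stands is within 7.3.2.

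**Responders may not truly be in control.** It is tempting to say that fully controlled patients are scored as relapsed. Counts inside a gap are unknown, and two missed 12-weekly visits leave 3 × 12 = 36 weeks between counts. The supportable statement is controlled at every observed visit. For the same reason, carrying response through such a gap without limit would err in the other direction.

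**Missed pairs should be rare.** Up to Week 52 the 7-day windows of 2-weekly visits abut, so an unscheduled count will usually fall in one of them. Protocol 6.3 asks for repeat tests when counts are not obtained, and 7.6.1 asks sites to follow up by telephone. A late draw recorded under its nominal visit may also count, since the window is introduced for unscheduled draws. These points lower the figures, particularly before Week 52; clustering of missed visits would raise them.

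**Which gaps count, and for how long.** Counting every missed pair from an early start of response would give larger figures, but the duration must include the qualifying 12 weeks, so an earlier gap cannot be the loss event. Week 152 is also a long horizon: Protocol 9.4 places the analysis when the last subject reaches Week 52 or discontinues, so only earlier enrollees would have data that far.

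**The consequence is limited.** Protocol 9.3 has duration of response estimated without comparison. That stands.

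**Conclusion.** The concern holds in limited form. As written, 7.3.2 can record a loss of response for which no raised count exists, and for a gap just before drug discontinuation or database freeze it gives two conflicting answers.

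The bias in the Kaplan-Meier estimate is downward. It is small by Week 52 and reaches about one always-controlled responder in ten only at 10% missed visits with follow-up to Week 152. These sizes rest on assumed miss rates, independence between visits and no unscheduled rescue.

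With few responders expected, especially on anagrelide, a single such event could visibly alter a curve. The primary endpoint, its test and alpha control are untouched. The point merits correction because the text is ambiguous and the repair is cheap; it does not threaten the trial's main conclusion.

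**What to change.** Amend SAP 7.3.2 as follows.

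- Loss of response requires 2 consecutive non-missing visits with platelets at or above 600 or WBC at or above 10 × 10⁹/L.
- Where 2 or more consecutive visits are missing after the qualifying window, the main curve censors at the last controlled assessment before the gap. A supplementary curve continues through the gap when the next count is controlled.
- The present missing-as-uncontrolled rule is kept as a sensitivity curve, and for deciding whether control is ongoing at Week 32, which otherwise would have no rule for a missing count.
- The censoring rule governs gaps that run up to drug discontinuation or database freeze.

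SAP 7.2.1 stays as it is. The cost is a few sentences and two additional Kaplan-Meier runs. The downside is that a true loss hidden in a gap may be missed; the sensitivity curve covers that.

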### **7.3.3. Individual Components of the Primary Endpoint**

The proportion of subjects who achieve a reduction of platelet counts to  $< 600 \times 10^9/L$  for at least 80% of biweekly assessments for a consecutive 12-week period between Weeks 32 and 52 will be summarized along with their 95% confidence interval.

The proportion of subjects who achieve a reduction of WBC counts to  $< 10 \times 10^9/L$  for at least 80% of biweekly assessments for a consecutive 12-week period between Weeks 32 and 52 will be summarized along with their 95% confidence interval.

## 9. SAFETY AND TOLERABILITY

[Appendix F](#) provides a list of data displays.

### 9.1. General Considerations

The analyses for this section will be provided for the safety population. Summary tables may be replaced with listings when appropriate. For instance, an AE frequency table may be replaced with a listing if it only contains a few unique preferred terms reported on relatively few subjects.

For vital sign and laboratory test values, a primary set of the safety analyses will be based on the safety population, and all safety data will be summarized by visit and by treatment group. Separate analyses will be conducted for crossover subjects, and only the assessments that occurred after the crossover will be summarized.

For safety events, a primary set of the analyses will be based on the safety population, and results will be summarized by treatment group up to the end of the randomization period. The end of the randomization period is defined as the earliest of discontinuation or the individual unblinding date. Separate analyses of safety events will be conducted for all subjects, including those who cross over to ruxolitinib from anagrelide and those who continue on ruxolitinib after unblinding. For crossover subjects, only safety events and assessments that occurred in the crossover period will be counted. For subjects originally taking ruxolitinib, safety events and assessments that occurred in both the randomization and open-label treatment periods will be counted. Results will be shown by treatment group (ruxolitinib and ruxolitinib after crossover).

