**Estimated Duration of Participation:**

Individual subject participation is expected to average 24 to 36 months, which includes the following:

**Screening period** (Day -35 to Day -8): Up to 28 days.

**Baseline (pretreatment) period** (Day -7 to Day -1): 7 days before the first dose of treatment (required for all eligible subjects to complete the daily symptom diary for 7 days before the first dose of study medication.

**Treatment period** (Day 1 through Week 52): Begins with first dose of either ruxolitinib plus anagrelide-placebo or anagrelide plus ruxolitinib-placebo (Day 1). The efficacy assessment period will be defined by collection of blood samples every 2 weeks between Weeks 32 and 52.

**Crossover and extension period:** Treatment with open-label ruxolitinib will continue until the study is concluded for subjects originally randomized to ruxolitinib who are receiving benefit from treatment or subjects originally randomized to anagrelide who cross over after unblinding treatment.

**Follow-up period:** 30 to 37 days after last dose of blinded study treatment or open-label study treatment.

**Estimated Number of Subjects:** Approximately 120 subjects will be randomized in a 1:1 manner to 1 of 2 treatment groups (approximately 60 subjects per group). Approximately 85 clinical sites will be used in the United States.

**Principal Coordinating Investigator:** [REDACTED], MD, PhD, MD [REDACTED]  
[REDACTED]

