Hydroxyurea (HU), with or without aspirin, is considered first-line therapy in most subjects with ET ([Cortelazzo et al 1995](#), [Harrison et al 2005](#)). Side effects of HU, which include oral ulcers, hyperpigmentation, skin rash, and nail changes, may lead to discontinuation of therapy and the need for alternative cytoreductive therapy. A small percentage of subjects will develop leg ulcers, nausea, diarrhea, or alopecia ([Gisslinger et al 2013](#), [Barbui and Finazzi 2005](#), [Latagliata et al 2012](#)). Thus, many subjects cannot remain on HU and require alternative cytoreductive therapies.

Anagrelide is an oral imidazoquinazoline derivative that may interfere with megakaryocyte proliferation and maturation, resulting in platelet underproduction ([Tomer 2002](#), [Mazur et al 1992](#)). Anagrelide is approved by the FDA for the treatment of patients with thrombocythemia, secondary to myeloproliferative disorders, to reduce the elevated platelet count and the risk of thrombosis and to ameliorate associated symptoms including thrombo-hemorrhagic events. In general, the drug is capable of reducing the platelet count to  $< 600 \times 10^9/L$  in more than 80% of previously treated and untreated subjects in a similar manner to HU ([Gisslinger et al 2013](#), [Harrison et al 2005](#), [Petitt et al 1997](#), [Chintagumpala et al 1995](#), [Balduini et al 1992](#)). Anagrelide has minimal effect on WBCs that may also be an important mediator of thrombotic risk ([Harrison et al 2005](#), [Bouchard and Tracy 2001](#), [Falanga et al 2000](#)). Anagrelide also does not appear to stop the progression of bone marrow fibrosis and hypercellularity in ET or

PV (Hultdin et al 2007). Toxicity of anagrelide is mainly related to the drug's direct vasodilatory and inotropic effects (Spencer and Brogden 1994, Abe Andes et al 1984). Anagrelide use in patients with ET has been associated with acquired idiopathic cardiomyopathy and must be given with caution in patients with known or suspected heart disease, which may limit its utility in the older patient (Jurgens et al 2004, Amabile and Spencer 2004). Thus, anagrelide is not tolerated or poorly tolerated in many subjects who would benefit from alternative options for platelet control.

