**Figure 1: Study Design**

#### **4.1.1. Options for the Open-Label Treatment Phase**

Subjects originally randomized to ruxolitinib with anagrelide placebo (Group A) who are receiving benefit from therapy can 1) continue receiving open-label ruxolitinib until the study is concluded or they meet discontinuation criteria, or 2) choose to discontinue therapy.

Subjects originally randomized to receive anagrelide plus ruxolitinib placebo (Group B) have 3 options: 1) they may cross over to begin receiving ruxolitinib if they meet eligibility criteria after consultation with the sponsor and may then continue until the study is concluded or they meet discontinuation criteria; 2) they may continue receiving anagrelide until the study is concluded or they meet discontinuation criteria; or 3) they can choose to discontinue therapy. Note that subjects originally randomized to Group B may cross over to receive ruxolitinib at any time during the open-label part of the study.

Subjects who will continue with the same active agent to which they were randomized will have a study visit at Week 56, at which time study drugs will switch over to open-label supplies (ruxolitinib or anagrelide) and then study visits every 12 weeks (Week 68, 80, etc). Subjects who were originally randomized to anagrelide (Group B) and who cross over to ruxolitinib will begin receiving ruxolitinib at the Week 56 visit. These subjects will have study visits at Weeks 1, 2, 3, 4, and every 4 weeks up to 52 weeks, then every 12 weeks thereafter. Subjects who initially remain on anagrelide after unblinding but choose to cross over to receive ruxolitinib at a later time will have study visits at Weeks 1, 2, 3, 4, and every 4 weeks up to 52 weeks, then every 12 weeks thereafter.

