#### 4.5. Overall Study Duration

The study begins when the first subject signs the ICF. The blinded treatment phase is complete and study data analysis can occur for the primary endpoint when all subjects have completed Week 52 or discontinued, and all study data through the Week 52 visit have been entered and the data cleaned and verified. The database will be frozen at this time for the initial data analysis to occur.

The study is completed when the last subject has reached Week 156 (approximately 3 years of treatment). Individual subject participation is expected to average 24 to 36 months.

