### 9.2.3. Adverse Event Summaries

An overall summary of AEs by treatment group will include the following:

- Number (%) of subjects reporting any TEAEs
- Number (%) of subjects reporting any SAEs
- Number (%) of subjects reporting any Grade 3 or higher TEAEs
- Number (%) of subjects reporting any treatment-related TEAEs
- Number (%) of subjects with TEAEs leading to temporary dose interruption
- Number (%) of subjects with TEAEs leading to dose reductions
- Number (%) of subjects with TEAEs leading to permanent discontinuation of study drug
- Number (%) of subjects with TEAEs leading to withdrawal from the study
- Number (%) of subjects who had a fatal TEAE

The following summaries will be produced by MedDRA term (if  $\leq 10$  subjects appear in a table, then a listing may be appropriate):

- Summary of TEAEs by system organ class and preferred term
- Summary of TEAEs by preferred term in decreasing order of frequency
- Summary of TEAEs by system organ class, preferred term, and worst CTCAE grade
- Summary of Grade 3 or higher TEAEs by system organ class and preferred term
- Summary of treatment-related AEs by system organ class and preferred term
- Summary of treatment-related AEs by system organ class, preferred term, and worst CTCAE grade
- Summary of TEAEs leading to death by system organ class and preferred term
- Summary of treatment-emergent SAEs by system organ class and preferred term
- Summary of treatment-emergent SAEs by preferred term in decreasing order of frequency
- Summary of treatment-related SAEs by system organ class and preferred term
- Summary of TEAEs leading to dose interruption by system organ class and preferred term
- Summary of TEAEs leading to dose reduction by system organ class and preferred term

- Summary of TEAEs leading to discontinuation of study drug by system organ class and preferred term
- Summary of TEAEs leading to withdrawal from the study by system organ class and preferred term
- Summary of treatment-emergent nonserious AEs by system organ class and preferred term

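### The all-ruxolitinib adverse event tables set crude percentages side by side over windows that differ by at least 56 weeks for equal total follow-up

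*SAP*

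**What the plan says.** SAP 9.1 describes two sets of safety-event tables. The primary set compares ruxolitinib with anagrelide up to the end of the randomization period, meaning discontinuation or individual unblinding, whichever comes first. A second set covers everyone who receives ruxolitinib and has two columns: ruxolitinib, and ruxolitinib after crossover.

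The counting windows of the second set differ. For the first column: "For subjects originally taking ruxolitinib, safety events and assessments that occurred in both the randomization and open-label treatment periods will be counted". For the second: "For crossover subjects, only safety events and assessments that occurred in the crossover period will be counted".

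Protocol 4.1.1 fixes when the second window can open. Group B subjects who "cross over to ruxolitinib will begin receiving ruxolitinib at the Week 56 visit" are the earliest starters. Others "may cross over to receive ruxolitinib at any time during the open-label part of the study". There is no individual end date. The protocol synopsis, under estimated duration of participation, says: "Treatment with open-label ruxolitinib will continue until the study is concluded". Protocol 4.5 places study completion at the last subject's Week 156.

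The measure in SAP 9.2.3 is a crude count and percentage, for example "Number (%) of subjects reporting any TEAEs". SAP 5.1 prescribes numbers and percentages for categorical variables generally. SAP Appendix F lists 17 adverse event tables for the All Ruxolitinib Treated Phase (3.2.18 to 3.2.34). The visible text contains no exposure-adjusted rate, time-to-first-event analysis or common time window for adverse events. Exposure in this phase has its own table (3.1.2). The text on events of special interest (SAP 9.2.2) is blacked out, so Table 3.2.34 cannot be judged.

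**The concern.** The percentage of subjects with at least one event rises with time at risk whenever events keep occurring. Two columns of the same drug, one counted from Day 1 and the other from Week 56 or later, will then differ even if the drug carries the same risk in both. A reader could conclude that ruxolitinib is safer when started after a year of anagrelide, or more harmful in subjects randomized to it, when the difference comes from the length of the window.

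The protocol itself gives reason to expect accrual. Section 1.2.3.2 reports that the numbers and proportions of adverse events rose, as expected, with longer follow-up in myelofibrosis. Section 1.5.1 describes deaths after 3 to 6 years and malignancies after 7 years of ruxolitinib in essential thrombocythemia. Long-term safety is the main information that the open-label phase can add, and these tables are where it will be read.

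**Working it through.** **Inputs.**
- First-column window: opens at Day 1 (SAP 9.1).
- Second-column window: opens at Week 56 or later (Protocol 4.1.1).
- Illustrative end: Week 156 (Protocol 4.5). This is the last subject's time point and not an individual limit, so earlier enrollees can be followed longer.
- Event rates: the documents give none. Those below are assumptions, equal in both columns and constant over time.

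**Step 1: windows.** 156 × 7 / 365.25 = 2.99 years, which reproduces the protocol's figure of about 3 years. A subject who crosses over at Week 56 has 156 − 56 = 100 weeks on ruxolitinib, an exposure ratio of 156/100 = 1.56. The gap is 56 weeks at any equal total follow-up and grows with later crossover.

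**Step 2: crude percentages at identical risk.** p = 1 − exp(−rate × weeks/52).

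| Assumed first-event rate per year | 156 weeks | 100 weeks |
|---|---|---|
| 0.1 | 25.9% | 17.5% |
| 0.3 | 59.3% | 43.8% |
| 0.6 | 83.5% | 68.5% |

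**Step 3: other data cuts.** Protocol 9.4 triggers the final analyses when the last subject reaches Week 52 or discontinues, so follow-up at that lock will vary between subjects. Assuming a 20% risk per 100 weeks, p(t) = 1 − 0.8^(t/100):

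| Total follow-up (weeks) | Weeks after crossover at Week 56 | From Day 1 | After crossover | Ratio |
|---|---|---|---|---|
| 80 | 24 | 16.3% | 5.2% | 3.1 |
| 104 | 48 | 20.7% | 10.2% | 2.0 |
| 156 | 100 | 29.4% | 20.0% | 1.47 |
| 208 | 152 | 37.1% | 28.8% | 1.3 |

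**Step 4: early-onset events.** If all events of a type occur soon after the first dose, inside both windows, the two percentages are equal and the problem disappears.

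**Step 5: does the remedy work?** Rate = −ln(1 − p) / person-years. After crossover: −ln(0.80) / (100 × 7/365.25) = 11.6 per 100 patient-years. From Day 1: −ln(1 − 0.294) / 2.99 = 11.6. The ratio is 1.00, against 1.47 for the crude percentages. Cutting both columns at the same time since first ruxolitinib dose also gives 1.00.

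**Step 6: the randomized phase.** Blinded treatment is planned for 52 weeks in both arms (Protocol 4.1). Assume a 20% risk per 52 weeks in each arm and discontinuation proportion d by Week 52. With h = −ln(0.8)/52 and g = −ln(1 − d)/52, the crude percentage is h/(h + g) × [1 − exp(−52(h + g))]. At d = 10% in both arms it is 19.0% in each. At 10% vs 30% it is 19.0% vs 16.9%, and at 10% vs 50% it is 19.0% vs 14.6%. A gap needs unequal discontinuation.

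**The case against.** The tables are openly labelled. SAP 9.1 calls them separate analyses, states each column's window and specifies no test, and Table 3.1.2 reports exposure. The columns are not a randomized contrast either: crossover subjects have reached Week 52, met eligibility criteria and been selected by the investigator after consultation with the sponsor. No adjustment for exposure makes the groups comparable. All of this stands. It limits what the columns can show, but it does not make the crude display a good one. Percentages printed side by side are read as a comparison, and a separate exposure table does not tell the reader how much of a difference is time at risk.

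The 56-week gap is also a statement about subjects with equal total follow-up, not about column averages. The randomized column keeps its early stoppers, whereas the crossover column by definition has none from the blinded year. The average gap could be narrower, and cannot be computed from the documents.

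A reader might infer something stronger: that the comparison of ruxolitinib with anagrelide, a secondary objective, is biased by the design. The documents do not support that. The all-ruxolitinib tables have no anagrelide column, and the anagrelide comparison is cut at the end of a randomized period of equal planned length. The protocol background does say that "anagrelide is not tolerated or poorly tolerated in many subjects", but this describes anagrelide use in general. Exclusion criterion 2 keeps out subjects who stopped earlier anagrelide because of an adverse event, and the documents forecast no discontinuation rate for either arm. Discontinuation also has outputs of its own: exposure in Table 3.1.1, a Kaplan-Meier plot of time to treatment discontinuation (Figure 4.2.3), and discontinuation for adverse events as a secondary endpoint.

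**Conclusion.** The concern holds for the all-ruxolitinib adverse event tables, which report crude percentages over unequal windows with no visible correction. In the illustration to Week 156, identical risk shows as 25.9% vs 17.5% at the lowest assumed rate and 83.5% vs 68.5% at the highest. At an assumed 20% per 100 weeks the ratio is 1.47, rising to about 3 at 80 weeks of total follow-up and falling to 1.3 at 208 weeks. These sizes rest on assumed constant, equal rates, crossover at exactly Week 56, and subjects followed for the same total time. Early-onset events would show little or no gap.

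For the randomized tables there is no imbalance by design. One would appear only if discontinuation differed between arms, and its size would depend on that difference. The issue is one of presentation in a descriptive safety analysis. It is worth correcting because the correction is cheap, and it leaves the primary safety comparison as planned.

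**What to change.** Amend SAP 9.1 and 9.2.3, and the matching tables in Appendix F, as follows.

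- For the all-ruxolitinib tables, show both groups over the same first 52 weeks after first ruxolitinib dose, censoring subjects with shorter follow-up.
- In the same tables, add first-event rates per 100 patient-years for four categories: any TEAE, SAEs, Grade 3 or higher TEAEs, and discontinuations of study drug for adverse events. Rates and confidence intervals for every preferred term are more than a trial of about 120 subjects needs.
- As support, give the same four overall rates by arm in the randomized phase. Fixing this in advance avoids choosing the measure after unblinding if discontinuation turns out unequal.
- State in a footnote that the two ruxolitinib columns are a non-randomized, descriptive comparison.

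The cost is programming and a few more tables. First and last dose dates are already used for exposure in SAP 6.4. Patient-year rates assume a roughly constant hazard: for events concentrated soon after the first dose, the longer exposure in the first column dilutes its rate and turns the distortion the other way. They should therefore be read together with the common-window view and not replace it.
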